5.5.2 Storage re-use, and destruction of pharmacodynamic samples

The primary pharmacodynamic (PD) samples will be kept in the AZ Biobank for 15 years for future needs.

Samples will be stored for a maximum of 15 years from the date of the Last Subject's Last Visit, after which they will be destroyed. The results of any investigation will be reported either in the Clinical Study Report itself or as an addendum, or separately in a scientific report or publication.

5.6 Biomarker analysis

The patient's consent to the use of donated biological samples is mandatory.

Biological samples (e.g., archived tumour samples and ctDNA) will be collected and may be analysed for exploratory biomarkers to assess correlations with disease activity, effects of study drug, clinical outcomes and toxicity.

Details on sample processing, handling, and shipment are provided in the Laboratory Manual.

The results of exploratory biomarker research will be reported separately and will not form part of the CSR.

5.6.1 Archived or fresh/recent tumour tissue required for correlative studies

All patients are required to provide archival or fresh tumour samples for study participation. The tumour samples will preferably be in the form of a block. If this is not possible, then up to 20 slides will be requested depending on the tumour type. Studies on these tumour tissues may include, but are not limited to, the analysis of genetic aberrations in the tumour that may be associated with response or resistance to AZD1775. Please see the Laboratory Manual for additional information around tumour requirements.

If the tumour tissue sample is insufficient for molecular analysis, the investigative site will be informed and additional tissue will be requested (refer to the Laboratory Manual).

The patients' molecular profiles will be established using a Sponsor-approved method and clinical laboratory (see Laboratory Manual).

A full report of the molecular biomarker panel will subsequently be made available to investigators upon individual request.

Further details on sample processing, handling, and shipment are provided in the Laboratory Manual.

5.6.2 Plasma isolation samples

Blood samples (20 mL) will be drawn to enable plasma isolation pre-dose as indicated in [Table 2](#), [Table 3](#), and [Table 4](#), at the end of treatment, at the FPV, and at disease progression for patients continuing treatment after FPV. The plasma may be analysed for biomarkers including, but not limited to, changes in cytokine levels as well as the presence of cell-free DNA in the blood, or circulating tumour-derived DNA (ctDNA). The studies on ctDNA may include, but are not limited to, determination of the amount of ctDNA in the blood and whether certain tumour-derived aberrations such as mutations are present and change after treatment with AZD1775.

5.6.3 On-treatment tumour biopsy

An on-treatment tumour biopsy is required for all patients with surface accessible lesions within 12 hours of one of the last AZD1775 doses taken on Day 4 or 5 or within the first 12 hours of Day 6 in Cycle 2 (Day 4 through 6) unless medically contraindicated on the scheduled day in the opinion of the investigator. The exact timing of the biopsy relative to the first dose of AZD1775 should be noted as described in the Laboratory Manual. Studies may include, but are not limited to, analysis of the downstream effects of Wee1 inhibition such as changes in the levels of phosphorylation of the Wee1 kinase substrate CDC2.

For the Wee1 inhibitor AZD1775, this means to demonstrate that following treatment of patients there is a measurable decrease from baseline in readouts of activity of the Wee1 kinase via analysis of the levels of phosphorylated CDC2 (pCDC2) in tumour samples. The collection of baseline and on-treatment biopsies is essential to guarantee the comparison of pCDC2 levels before and during treatment and to provide evidence that patients receive a biologically active dose.

5.6.4 Storage, re-use and destruction of biological samples

Samples will be stored for a maximum of 15 years from the date of the Last Patient's Last Visit, after which they will be destroyed. The results of this biomarker research will be reported either in the Clinical Study Report itself or as an addendum, or separately in a scientific report or publication. The results of this biomarker research may be pooled with biomarker data from other studies with the study drug to generate hypotheses to be tested in future research.

5.6.5 Labelling and shipment of biological samples

The Principle Investigator (PI) ensures that samples are labelled and shipped in accordance with the Laboratory Manual and the Biological Substance, Category B Regulations (materials containing or suspected to contain infectious substances that do not meet Category A criteria). See [Appendix B](#) 'IATA 6.2 Guidance Document' (International Air Transport Association).

Any samples identified as Infectious Category A materials are not shipped and no further samples will be taken from the patient unless agreed with AstraZeneca or designee and appropriate labelling, shipment and containment provisions are approved.

5.6.6 Chain of custody of biological samples

A full chain of custody is maintained for all samples throughout their lifecycle.

The PI at each centre keeps full traceability of collected biological samples from the patients while in storage at the centre until shipment or disposal (when appropriate).

The sample receiver keeps full traceability of the samples while in storage and during use until used or disposed of or until further shipment and keeps documentation of receipt of arrival.

AstraZeneca, the study sponsor, keeps oversight of the entire life cycle through internal procedures, monitoring of study sites and auditing of external laboratory providers.

Samples retained for further use are registered in the AstraZeneca Biobank during the entire life cycle.

5.6.7 Withdrawal of Informed Consent for donated biological samples

If a patient withdraws consent to the use of donated biological samples, the samples will be disposed of/destroyed, and the action documented. If samples are already analysed, AstraZeneca or its designee is not obliged to destroy the results of this research.

The PI:

- Ensures patients' withdrawal of informed consent to the use of donated samples is notified immediately to AstraZeneca or its designee
- Ensures that biological samples from that patient, if stored at the study site, are immediately identified, disposed of /destroyed, and the action documented
- Ensures the laboratory(ies) holding the samples is/are informed about the withdrawn consent immediately and that samples are disposed of/destroyed, the action documented and the signed document returned to the study site
- Ensures that the patient and AstraZeneca or its designees are informed about the sample disposal.

AstraZeneca or its designee ensures the central laboratory(is) holding the samples is/are informed about the withdrawn consent immediately and that samples are disposed of/destroyed and the action documented and returned to the study site.

AstraZeneca ensures that biological samples are destroyed at the end of a specified period as described in the informed consent.

6. SAFETY REPORTING AND MEDICAL MANAGEMENT

The Principal Investigator is responsible for ensuring that all staff involved in the study are familiar with the content of this section.

6.1 Definition of adverse events

An AE is the development of an undesirable medical condition or the deterioration of a pre-existing medical condition following or during exposure to a pharmaceutical product, whether or not considered causally related to the product. An undesirable medical condition can be symptoms (e.g., nausea, chest pain), signs (e.g., tachycardia, enlarged liver) or the abnormal results of an investigation (e.g., laboratory findings, electrocardiogram). In clinical studies, an AE can include an undesirable medical condition occurring at any time, including run-in or washout periods, even if no study treatment has been administered.

The term AE is used to include both serious and non-serious AEs.

For cases where it could be suspected that a tissue-derived medicine has been contaminated by a pathogen, information about any of the above conditions (including infection) should be collected. Any deterioration of disease targeted in the study and associated symptoms should not be regarded as an adverse event.

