5.2.2 Physical examination

A complete physical examination will be performed and will include an assessment of the following: general appearance; abdomen, skin, head and neck (including ears, eyes, nose and throat); lymph nodes and thyroid; and respiratory, cardiovascular, musculo-skeletal (including spine and extremities), and neurological systems.

If new or aggravated physical findings imply deterioration compared with baseline, the finding should be reported as an AE (Section 6). Performance status will be assessed using the ECOG performance status criteria (see Study Plan [Table 2](#), [Table 3](#), and [Table 4](#)).

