6.3.6 Adverse events based on examinations and tests

The results from protocol mandated laboratory tests and vital signs will be summarised in the CSR. Deterioration as compared to baseline in protocol-mandated laboratory values, vital signs should therefore only be reported as AEs if they fulfil any of the SAE criteria or are the reason for discontinuation of treatment unless clearly due to the progression of disease under study.

If deterioration in a laboratory value/vital sign is associated with clinical signs and symptoms, the sign or symptom will be reported as an AE and the associated laboratory result/vital sign will be considered as additional information. Wherever possible the reporting Investigator uses the clinical rather than the laboratory term (e.g., anaemia versus low haemoglobin value). In the absence of clinical signs or symptoms, clinically relevant deteriorations in non-mandated parameters should be reported as AE(s).

Deterioration of a laboratory value, which is unequivocally due to disease progression, should not be reported as an AE/SAE.

Any new or aggravated clinically relevant abnormal medical finding at a physical examination as compared with the baseline assessment will be reported as an AE.

Examples of these are marked haematological and other laboratory abnormalities, and certain events that lead to intervention (other than those already classified as serious), dose reduction or significant additional treatment.

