6.3.8 Disease progression

Disease progression can be considered as a worsening of a patient's condition attributable to the disease for which the IP is being studied. It may be an increase in the severity of the disease

under study and/or increases in the symptoms of the disease. The development of new, or progression of existing metastasis to the primary cancer under study should be considered as disease progression and not an AE. Events which are unequivocally due to disease progression should not be reported as an AE during the study.

Events including diagnosis or signs and symptoms or the abnormal results of an investigation including those leading to hospitalization, which constitute or result from:

- a) ‘unequivocal progression’ (i.e., representative of overall disease status change, not a single lesion increase) of non-measurable/non-target disease,

or

- b) progression of malignancy under study (target disease) as determined per RECIST 1.1 criteria, should not be reported as AEs or SAEs.

Progression of the malignancy under study, including signs and symptoms of progression, should not be reported as a serious adverse events. Hospitalizations due to signs and symptoms of disease progression should not be reported as serious adverse events.

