Patients with ‘symptomatic deterioration’ requiring discontinuation of treatment without objective evidence of disease progression at that time should continue to undergo tumour assessments where possible until objective disease progression is observed.

Evaluation of objective visit response

The objective visit response will be derived using the algorithm shown below.

Objective visit response

Target lesions	Non-Target lesions	New Lesions	Objective response
CR	CR	No	CR
CR	NA	No	CR
NA	CR	No	CR
CR	Non CR/Non PD	No	PR
CR	NE	No	PR
PR	Non PD or NE	No	PR
SD	Non PD or NE	No	SD
NE	Non PD or NE	No	NE
PD	Any	Yes or No	PD
Any	PD	Yes or No	PD
Any	Any	Yes	PD

CR = complete response, PR = partial response, SD = stable disease, PD = progressive disease, NE = not evaluable, NA = not applicable (only relevant if there were no NTLs at baseline).

CONFIRMATION OF RESPONSE

In the D6015C00003 study, imaging for confirmation of response (CR or PR) should be performed at next scheduled visit (certainly no less than 4 weeks) following the date the criteria for response were first met.

SPECIFICATIONS FOR RADIOLOGICAL IMAGING

These notes are recommendations for use in clinical studies. The use of standardized protocols for CT and MRI allows comparability both within and between different studies, irrespective of where the examination has been undertaken.

CT Scans

CT scans of the chest, abdomen, and pelvis should be contiguous throughout all the anatomic region of interest.

The most critical CT image acquisition parameters for optimal tumour evaluation using RECIST 1.1 are anatomic coverage, contrast administration, slice thickness, and reconstruction interval.

Anatomic coverage: Optimal anatomic coverage for most solid tumours is the chest, abdomen and pelvis. Coverage should encompass all areas of known predilection for metastases in the disease under evaluation and should additionally investigate areas that may be involved based on signs and symptoms of individual patients. Because a lesion later identified in a body part not scanned at baseline would be considered as a new lesion representing disease progression, careful consideration should be given to the extent of imaging coverage at baseline and at subsequent follow-up time points. This will enable better consistency not only of tumour measurements but also identification of new disease.

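### The protocol uses different thresholds for leaving disease-related events out of the AE record, so an event probably but not unequivocally due to the tumour may or may not count as a TEAE or SAE

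*Protocol*

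**What the plan says.** The rules sit in five places.

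- **Section 6.1**, at the end of the AE definition: "Any deterioration of disease targeted in the study and associated symptoms should not be regarded as an adverse event". Neither certainty nor objective progression is required.
- **Section 6.3.8** is mixed. It opens with a broad description of progression that takes in increased symptoms. For AEs it then says: "Events which are unequivocally due to disease progression should not be reported as an AE during the study". Two limbs follow: unequivocal progression of non-target disease, and "progression of malignancy under study (target disease) as determined per RECIST 1.1 criteria, should not be reported as AEs or SAEs". The last paragraph drops the certainty limit for serious events: "Progression of the malignancy under study, including signs and symptoms of progression, should not be reported as a serious adverse events". A matching sentence on hospitalisations also lacks it.
- **Section 6.3.6** exempts laboratory and vital-sign deterioration only when it is clearly due to progression, and laboratory deterioration again only when unequivocally so. For physical findings it has no disease exception: "Any new or aggravated clinically relevant abnormal medical finding at a physical examination as compared with the baseline assessment will be reported as an AE".
- **Section 5.2.2** gives a similar rule: "If new or aggravated physical findings imply deterioration compared with baseline, the finding should be reported as an AE". It refers to Section 6.
- **Section 6.3.10** exempts from SAE reporting only deaths unequivocally due to progression. Where a death is not clearly due to progression, the AE that caused it is reported as an SAE.

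Section 6.2 defines an SAE as an AE meeting seriousness criteria, and Section 8.3.4 defines a TEAE as an AE with on-treatment onset. Both inherit the AE definition. Section 2.2 names TEAEs and SAEs as the outcome measures of the safety and tolerability objective.

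**The concern.** The rules part on events that are plausibly, but not certainly, caused by the tumour. Section 1.2.3 lists anaemia, nausea, vomiting, decreased appetite, fatigue and gastrointestinal haemorrhage among the known reactions to or potential risks of AZD1775. All of these can also arise from advanced cancer, so the uncertain group may include real drug effects.

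The study has no control arm against which uneven recording would show. Two sites can each follow the protocol and treat the same event differently. An event left out of the AE record carries no AE grade or causality entry, so it cannot be reclassified at analysis. It also never reaches the guidance in Appendix A, which tells investigators to treat ambiguous cases as a reasonable possibility of causation.

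**Working it through.** No design figure depends on this wording, so the check sets the rules side by side and runs specific cases through them.

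| Rule | What is excluded from AE or SAE reporting | Certainty required |
|---|---|---|
| 6.1 | Deterioration of the target disease and its symptoms | None stated |
| 6.3.8, AE sentence | Events due to progression | Unequivocal |
| 6.3.8, SAE and hospitalisation sentences | Signs, symptoms and admissions due to progression | None stated |
| 6.3.6, laboratory values | Deterioration due to progression | Clear or unequivocal |
| 6.3.10, deaths | Death due to progression | Unequivocal |
| 6.3.6 and 5.2.2, physical findings | Nothing | Not applicable |

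**Case 1: a newly enlarged liver in a patient with liver metastases, thought to be tumour-related.** Section 6.1 itself names an enlarged liver as an example of an AE sign. Under 6.3.6, if clinically relevant, and under 5.2.2, it is an AE. Under the last sentence of 6.1 it is not. Under the AE sentence of 6.3.8 the answer depends on whether the cause is unequivocal. This is a direct conflict.

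**Case 2: symptomatic deterioration.** Appendix E describes patients with symptoms "requiring discontinuation of treatment without objective evidence of disease progression at that time". Under 6.1, symptoms put down to the disease are not AEs. Under 6.3.8, neither limb is met, which points to recording them, but the section's opening description could cover them. Either choice can be defended.

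**Case 3: the Case 2 patient is admitted to hospital.** An admission meets a seriousness criterion in 6.2, but only an AE can be an SAE. Under 6.1 there is no AE. Under 6.3.8 the AE sentence points to recording and the hospitalisation sentence points away from it. Again the protocol supports both answers.

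**Case 4: a death probably, but not clearly, due to progression.** Section 6.3.10 requires the causing AE to be reported as an SAE. If the cause was deterioration of the disease, 6.1 says there is no AE to report.

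**Weight of one patient.** Table 12 plans 3 to 6 patients per cohort, and Section 7.2.4 plans at least 12 at the MTD/RP2D. One patient with an event counted or omitted moves the incidence by 1/3 = 33, 1/6 = 17 or 1/12 = 8 percentage points. This holds for any single event in groups of these sizes. It shows sensitivity and does not estimate how often the problem occurs.

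**The case against.** The best defence is that 6.1 is the general definition and 6.3.8 its operating rule, so the two are read together. Calling something disease deterioration is already an attribution, and 5.2.2 defers to Section 6. This eases the tension between 6.1 and 6.3.8 but does not remove it. The physical-finding rule in 6.3.6 is itself inside Section 6 and lacks the exception that the laboratory rule beside it has, and 6.3.8 does not hold to one threshold.

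The defence does rule out several stronger readings that a reader might infer.

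- **That a hospitalisation without objective progression is plainly an SAE under 6.3.8.** The hospitalisation sentence sets no condition of objective progression, so this is ambiguous.
- **That every worsened physical finding is an AE.** Section 6.3.6 limits its rule to clinically relevant findings, and 5.2.2 refers to Section 6.
- **That the primary outcome is compromised.** Section 7.2.2 already excludes from DLTs toxicities attributable to the disease. Under 7.2.3, DLTs go to the Medical Monitor within 24 hours of first knowledge.
- **That nothing survives for an event left out.** Protocol-mandated laboratory and vital-sign results are summarised whatever their AE status (6.3.6), the reason for stopping treatment is recorded (4.3), and deaths due to progression are documented in the eCRF (6.3.10). What is lost is the AE entry with its grade and causality.
- **That reported rates are biased downward overall.** The wording of 6.1 pushes counts down, while the physical-finding rules push them up. The net direction is not established.

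It is also fair to say that all schedules are closed to enrolment at Version 5, and that after the Final Protocol Visit only SAEs, pregnancies and overdoses are collected. A change now would affect little of the dose-escalation data and could put two recording rules into one dataset.

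**Conclusion.** The inconsistency is real and lies in the current text. Events probably but not unequivocally due to the disease, including symptomatic deterioration without objective progression, can be counted or omitted as TEAEs, and as SAEs through 6.2. This affects the consistency of the secondary safety outcome.

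The size is unknown because the documents give no rate for such events; the only figures available are the single-patient weights of 33, 17 and 8 percentage points. The conclusion assumes that some events of uncertain cause occur, which the overlap between the listed drug risks and symptoms of advanced cancer makes likely, and that sites would not all resolve the wording in the same way. No effect on the primary DLT outcome is shown. The point should be corrected, but it does not undermine the determination of the MTD.

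**What to change.** Reconcile 6.1, 6.3.8, 6.3.6 and 5.2.2 to the threshold the protocol already uses in the AE sentence of 6.3.8, the laboratory rule of 6.3.6 and the death rule of 6.3.10. Only events unequivocally due to disease progression are not AEs or SAEs; all others are recorded with grade and causality, including symptomatic deterioration without objective progression. In practice:

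- replace the last sentence of 6.1 with this limit;
- put the same limit on the SAE and hospitalisation sentences in the last paragraph of 6.3.8;
- add the same exception to the physical-finding rules in 6.3.6 and 5.2.2.

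The cost is protocol wording and slightly more AEs and SAEs recorded, so somewhat less favourable rates. Because enrolment is closed, the CSR should state the date from which the harmonised rule applied, so that readers know which events were collected under which wording.

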6.2 Definitions of serious adverse event

A serious adverse event (SAE) is an AE occurring during any study phase (i.e., run-in, treatment, washout, and follow-up), that fulfils one or more of the following criteria:

- Results in death
- Is immediately life-threatening
- Requires in-patient hospitalisation or prolongation of existing hospitalisation
- Results in persistent or significant disability/incapacity or substantial disruption of the ability to conduct normal life functions
- Is a congenital abnormality or birth defect
- Is an important medical event that may jeopardise the patient or may require medical intervention to prevent one of the outcomes listed above.

For further guidance on the definition of a SAE, see [Appendix A](#) to the CSP.

